11.4.2 Sample Size Re-calculation

Once intra-patient CV is identified, sample size re-calculation will be performed using nQuery 7.0 with the following parameters:

- Power = 90%
- Expected ratio = 0.88 to 1.12
- Lower equivalence limit = 0.8
- Upper equivalence limit = 1.25
- Test significance level alpha (one-sided) = 0.05
- CV between subjects = 1.21 (assumption from the protocol)
- CV within subjects = new number calculated from the above mentioned model based on the actual interim data

The results of the 2 new sample size estimates (one based on data from all treatments and the other based on the 2 “closest” data values) will be available after using the above parameters. The estimate of the ratio of the means demonstrated in the pivotal PK study will help inform which expected ratio will be used in the final sample size chosen.

Sponsor: Lupin Inc.
Protocol no: TB-DPI-301

11.5 Results of the Interim Analysis

The final interim analysis report was dated 01Sep2017, and is attached in [Appendix 3](#).

A total of 122 (of the 150) patients had 3 treatment periods with evaluable AUC data, and these data were included in the “closest” AUC analysis. Based on the results, the intra-patient CV was 0.3642 and the between-patient CV was 1.210. The table below summarizes the crossover design of two one-sided tests (TOST) for difference or ratio of means:

	Protocol	Closest AUC (N=122)		
		Low ratio	Ratio=1	High ratio
Test significance levels, α (one-sided)	0.050	0.050	0.050	0.050
Lower equivalence limit for μ_T / μ_R, D_L	0.800	0.800	0.800	0.800
Upper equivalence limit for μ_T / μ_R, D_U	1.250	1.250	1.250	1.250
Expected ratio, μ_T / μ_R	1.000	0.880	1.000	1.120
Coefficient of variation between subjects, CV_B	1.210	1.210	1.210	1.210
Coefficient of variation, intrasubject, CV_i	0.600	0.3642	0.3642	0.3642
Power (%)	90	90	90	90
n total	178	372	78	220

Results obtained from nQuery Advisor® 7.0

Based on the results, sample size estimates range from:

- a total of 372 across the six treatment sequences if the expected ratio of test to reference is 0.88
- a total of 220 patients across the six treatment sequences if the expected ratio of test to reference is 1.12

Assuming an expected ratio of means of 0.90 based on results from the pivotal PK study, an estimated 238 per-protocol patients would be needed to demonstrate equivalence between the test and reference products. Therefore, the Sponsor plans to randomize a total of approximately 378 patients (instead of 240 patients specified in the protocol with Amendment 1, dated 11May2017), to allow for a potential 30% withdrawal rate or loss from the per-protocol population due to protocol deviations.

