## 6.6 REPLACEMENT OF PATIENTS WHO WITHDRAW OR ARE DISCONTINUED

Patients who withdraw, are discontinued, or are lost to follow-up will not be replaced. However, the final number of patients to be randomized will be determined following the blinded interim analysis. The rate of patient early termination will be considered during the blinded interim analysis to help define the final number of patients to be randomized.

The date the patient is withdrawn from the study and the reason for discontinuation will be recorded in the eCRF. If there are multiple reasons for early discontinuation, the worst case scenario should be chosen.

If a patient is withdrawn because of an AE, the event will be followed until the medical condition returns to baseline or is considered stable or chronic. Discontinuation of patients due to AEs, including those due to abnormal laboratory results, should be promptly reported to Lupin Inc.

If a patient is lost to follow-up (fails to return for study visits), a reasonable effort should be made to determine why the patient failed to return. The occurrence of lost to follow-up will be documented in the eCRF.

Every effort should be made for all randomly assigned patients prematurely discontinuing, regardless of cause, to undergo final evaluation procedures, in accordance with the early termination (ET) visit as described in [section 9.3.5](#).

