The goal of the study is to complete 180 patients per protocol. With a sample size in each of the 6 sequence groups of 30, for a total sample size of 180, a crossover design will have 90% power to reject both the null hypothesis that the ratio of the test mean to the standard mean is below 0.80 and the null hypothesis that the ratio of test mean to the standard mean is above 1.25 (ie, that the test and standard are not equivalent), in favor of the alternative hypothesis that the means of the 2 treatments are equivalent, assuming that the expected ratio of means is 1.00, the between-patient coefficient of variation is 1.21, the intra-patient coefficient of variation is 0.60. In order to allow for a potential 30% premature withdrawal rate or loss from the PP population due to protocol deviations, 240 patients will be randomized in total, 40 to each of the 6 treatment sequences.

As no estimates of within-patient variability were available in the public domain, a blinded interim analysis will be conducted in order to assess the within-patient variability. The blinded interim analysis will be done to ascertain if an increase in sample size is necessary maintain 90% power to complete the study with a 90% CI for the relative bioavailability of the Test (T) to the Reference (R) product inside of the pre-specified interval 0.80-1.25.

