7.2 Randomization

Patients will be randomly assigned to the treatment sequences by means of a computer generated randomization list after confirmation of all eligibility criteria. The randomization list and study medication will be assigned via interactive response technology (IRT). Y-Prime Inc. will be responsible for generating the randomization schedule.

The randomization scheme utilized in TB-DPI-301 will be central. A total of 240 patients will be randomized in a ratio of 1:1:1:1:1:1 to the 6 treatment sequences based on a Williams design Latin square in the cross-over design shown in [Table 1](#).

Additionally, on each study day, as this is a double-dummy study, the order of administration of the LUPINHALER and HANDIHALER will be assigned based on even/odd calendar days. On odd calendar days (eg, 1, 3, 5, 29, 31), the LUPINHALER will be dosed first. On even calendar days (eg, 2, 4, 6, 28, 30), the HANDIHALER will be dosed first.

A subset of approximately 120 patients (at select investigational centers) will be enrolled into the open-label phase of the study (Part 2). These patients will not be randomized and all patients in Part 2 will receive Lupin Tiotropium Bromide Inhalation Powder.

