11.4.1 Intra-patient CV Estimation

In order to perform the interim sample size re-estimation (by nQuery7), the between-subject CV and the intra-subject CV need to be estimated using the interim data:

- Between-subject CV (CV_B) = σ_B / μ_R
- Intra-subject CV (CV_I) = σ_I / μ_R

Where σ_B is between-subject variance, σ_I is intra-subject variance and μ_R is the Least Square Mean (LSMean) of the reference (SPIRIVA) treatment.

To get estimates for σ_B , σ_I and μ_R , a mixed model can be used with a fixed effect for period and a random effect for patient using the PP population. The typical crossover model fixed effects for treatment and sequence are not included because the treatment codes are to remain blinded.

The SAS procedure to be used is:

```
proc mixed data=interim;
  class usubjid period;
  model Baseline-adjusted FEV1 AUC0-24h = period/ solution;
  random usubjid;
run;
```

where

- usubjid = patient
- period = treatment period

Sponsor: Lupin Inc.
Protocol no: TB-DPI-301

In the SAS output, the covariance (COV) estimate of σ_B will be called “Usubj_{id}” and σ_1 will be called “Residual”. Normally we estimate μ_R as the LSMeans for the reference (SPIRIVA) treatment, however, since this is a blinded estimation, we could instead use the estimate of CV_B from the Protocol as: $\mu_R = \sigma_B / 1.21$. Then, we use that estimate of μ_R to estimate $CV_1 = \sigma_1 / \mu_R$.

One downside of this approach is that it includes placebo which will almost surely inflate the intra-subject variance (and hence CV_1). The effect could be dramatic if the two active treatments are efficacious (i.e., much different from placebo). It should not affect between-subject variance.

To address this concern, 2 methods will be used to estimate the intra-subject variability and CV:

- Use the subject’s AUC values from all 3 treatments to estimate the intra-subject CV. This method will provide a liberal (i.e., likely too large) sample size estimate since the placebo data will increase the intra-subject CV.
- Only use the data from the two “closest” AUC values from each subject’s data to estimate the intra-subject CV. This approach mimics the inclusion of only the two active treatments in the sample size re-estimation (i.e., akin to excluding placebo). This method will produce a conservative (ie, likely too small) sample size estimate.

A decision on the sample size re-estimation will be made based on the results from the above 2 methods.

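### SAP 11.5: about 378 randomized does not follow from 238 per-protocol patients and 30% loss (that gives 340), the original 240 for 180 allows 25%, and SAP 7.2 still says 240

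*SAP*

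**What the plan says.** SAP 11.5 reports the blinded interim result. Taking a test-to-reference ratio of 0.90 from the pivotal PK study and the intra-patient CV of 0.3642 from the closest-AUC method, it concludes that "an estimated 238 per-protocol patients would be needed to demonstrate equivalence between the test and reference products". The next sentence presents the number to randomize as a consequence of this: "approximately 378 patients (instead of 240 patients specified in the protocol with Amendment 1, dated 11May2017), to allow for a potential 30% withdrawal rate". The same allowance is meant to cover exclusions from the per-protocol set for deviations.

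The original plan uses the same rate. The per-protocol target was 180, and Protocol 11.2 gives the reasoning: "allow for a potential 30% premature withdrawal rate or loss from the PP population due to protocol deviations, 240 patients will be randomized". The Protocol synopsis, Protocol section 6 and SAP 7.1 repeat this set of figures.

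SAP 7.2, in current text, says "A total of 240 patients will be randomized in a ratio of 1:1:1:1:1:1 to the 6 treatment sequences".

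Two other passages say what should feed the final number. Protocol 6.6: "The rate of patient early termination will be considered during the blinded interim analysis to help define the final number of patients". SAP 11.4.1, after describing an all-treatments method and a closest-AUC method for the intra-patient CV: "A decision on the sample size re-estimation will be made based on the results from the above 2 methods".

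**The concern.** Three figures set the size of this trial: the per-protocol patients needed, the expected loss, and the number randomized. Any two fix the third. In SAP 11.5 they do not agree, and in the original plan they disagree in the opposite direction, so a single stated rate of 30% stands for two different allowances.

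The increase from 240 to about 378 is 138 patients, decided mid-trial in a pivotal bioequivalence study. A reader should be able to reproduce it from the reason given, and cannot. The SAP also carries two totals to randomize, 240 in section 7.2 and about 378 in section 11.5.

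A reader might take the gap between 238 and what 378 yields at 30% loss as a safety margin. That would be unsafe, because 238 rests on the closest-AUC CV, of which SAP 11.4.1 says "This method will produce a conservative (ie, likely too small) sample size estimate".

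**Working it through.** **Inputs.** SAP 11.4.2 and 11.5: one-sided alpha 0.05, equivalence limits 0.80 and 1.25, target power 90%, between-patient CV (CV_B) 1.21, intra-patient CV (CV_I) 0.60 originally and 0.3642 at the interim, expected ratio 1.00 originally and 0.90 after the interim, 238 per-protocol, about 378 randomized, 30% loss. Protocol 11.2 and SAP 7.1: 180 per-protocol, 240 randomized, 30% loss.

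**Step 1. Reproduce the per-protocol numbers.** The method is two one-sided tests on the ratio of means in a crossover, with n − 2 degrees of freedom and, at limit t, in units of the reference mean squared,

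var(T − t·R) = [(1 + t²)·CV_I² + (1 − t)²·CV_B²] / n.

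For n = 238 at the lower limit: (1.64 × 0.3642² + 0.04 × 1.21²)/238 = (0.2175 + 0.0586)/238 = 0.00116, so the standard error is 0.0341 and (0.90 − 0.80)/0.0341 = 2.94.

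| Ratio | CV_I | n in SAP 11.5 | Power computed |
|---|---|---|---|
| 1.00 | 0.60 | 178 | 90.2% |
| 0.88 | 0.3642 | 372 | 90.1% |
| 1.00 | 0.3642 | 78 | 90.8% |
| 1.12 | 0.3642 | 220 | 90.0% |
| 0.90 | 0.3642 | 238 | 90.0% |

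All five are reproduced, so 238 is sound on its stated inputs.

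**Step 2. From per-protocol to randomized.** The formula is randomized = per-protocol / (1 − loss).

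- 238 / 0.70 = 340; six equal sequences of 57 make 342.
- Loss implied by 378: 1 − 238/378 = 37.0%.
- Per-protocol yield of 378 at 30% loss: 378 × 0.70 = 264.6, taken as 264.
- Unexplained: 378 − 342 = 36 to 378 − 340 = 38, about 10% of 378.

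Other routes also miss 378. A simple mark-up gives 238 × 1.30, about 310. The original proportion gives 238 × 240/180 = 317. The only interim count in SAP 11.5 is "A total of 122 (of the 150) patients had 3 treatment periods with evaluable AUC data". That leaves 28 of 150 (18.7%) without three evaluable periods; it is not a full loss rate, and taken alone it would give 238/(122/150) = 293. A further 10% on top of 30% does fit, since 340/0.90 = 378, but the supplied text states no such allowance.

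**Step 3. The original plan.**

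- 1 − 180/240 = 25.0%, not 30%.
- 240 × 0.70 = 168, not 180.
- 180 / 0.70 = 257.1, so 258.

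Power at ratio 1.00 and CV_I 0.60 is 90.6% with 180 and 88.1% with 168, against the stated 90%.

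**Step 4. What 264 is worth.** Power at ratio 0.90 and CV_B 1.21. CV_I values above 0.3642 are an assumed range, because the documents do not give the size of any understatement.

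| CV_I | n = 238 | n = 264 |
|---|---|---|
| 0.3642 | 90.0% | 92.5% |
| 0.40 | 85.8% | 88.8% |
| 0.45 | 79.3% | 82.8% |

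With 264, power falls to 90.0% at CV_I 0.389. A modest understatement of the CV therefore uses up the apparent margin.

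**The case against.** The strongest reply is that the number may be right and only the 30% out of date. SAP 11.5 attaches the interim report as Appendix 3, which is not in the supplied text and may hold the early-termination rate and the all-treatments result. If the 150 patients at the interim had all completed Part 1, the 18.7% is loss after completion, and about 22.5% earlier withdrawal would bring the total to 37% (1 − 0.63/0.813). No supplied passage gives that withdrawal rate, but Protocol 6.6 intended early termination to count. This stands as a possible explanation. Nothing can be held against the plan for what Appendix 3 may contain. It does not rescue the sentence in SAP 11.5, which gives 30% as the reason.

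Second, 378 exceeds 340, so no power is lost on the stated assumptions, and neither the analysis nor error control changes. That is correct, and it limits the weight of the point.

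Third, the original 240 is superseded, and 180 × 1.30 = 234, rounded up to 40 per sequence, may be its source. That is plausible, but such a mark-up still does not cover a 30% loss, and the same rule gives about 310 from 238. SAP 11.5 does name 240 as the figure being replaced, so a reader of the whole SAP can tell which total is current. Section 7.2 nevertheless states the old one as the plan.

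Fourth, the possible understatement of CV_I is already disclosed in SAP 11.4.1 and is separate from the inflation step. That is true. It matters here only because it stops the difference between 238 and 264 being read as spare.

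**Conclusion.** The point holds. On the plan's own figures, 30% loss from 238 requires 340 randomized (342 in equal sequences). About 378 is a 37% allowance, so 36 to 38 patients are unexplained. The original 240 for 180 is a 25% allowance. SAP 7.2 was not updated.

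The arithmetic in the inflation step needs no assumption beyond the stated figures. The power figures assume CV_B 1.21 and ratio 0.90; the 92.5% for 264 also depends on CV_I being 0.3642. This is an inconsistency in the reasoning for the trial's size. It does not threaten validity, and 378 is not shown to be too few or too many. It should be corrected, since the number randomized is one the trial relies on.

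**What to change.** **SAP 11.5.** Make the allowance match the number, in one of two ways:

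- say that 378 randomized reaches 238 per-protocol patients with up to 37% loss, or about 264 at 30% loss; or
- have the sponsor give the actual basis for 378, including any early-termination rate seen at the interim and the all-treatments result if it was used, by reference to Appendix 3 if they are there.

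If a power is quoted for 264, state that 92.5% applies at ratio 0.90 and is conditional on CV_I 0.3642, and repeat the SAP 11.4.1 caveat on the closest-AUC method. Do not describe the margin above 238 as spare.

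**SAP 7.2.** Replace 240 with about 378 (378/6 = 63 per sequence).

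**Where 240 stays as the original plan** (SAP 7.1; the Protocol synopsis, section 6 and 11.2 if the protocol is next amended), say that it allows for 25% loss.

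**Cost.** Wording only, in the SAP before database lock and in the protocol at its next amendment if there is one. No additional patients.

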12.0 Data Review

Final data for analysis should always be cleaned prior to receipt by Clinical Programming. The purpose of this section is to indicate the history of the data and the process used to ensure that the data are acceptable for statistical analysis prior to database lock.

12.1 Data Handling and Transfer

PRA prepares and delivers electronic media to each site of their respective subjects' eCRFs and a complete set of subject eCRFs are delivered to each site and Lupin Inc.

The data in the following table will be provided by third-party vendors:

Data Type	Vendor
Central Lab	Eurofins

Sponsor: Lupin Inc.
Protocol no: TB-DPI-301

Central Spirometry	ERT
ECG	ERT
eDiary	ERT
Randomization	YPrime

All of the study data will be provided in SAS[®] dataset format (SAS version 9.4 or later) and converted to Study Data Tabulation Model (SDTM) version 1.4 using the Study Data Tabulation Model Implementation Guide (SDTMIG) Version 3.1.4.

12.2 Data Screening

Review of 2 pre-freeze TFL dry runs allow for further data screening prior to lock. The pre-freeze TFL will be discussed with the sponsor in a data review meeting to identify any final data issues and seek corrections prior to database lock. The PRA biostatistician and the sponsor must approve database lock.

13.0 Statistical Methods

The statistical analyses will be reported using summary tables, figures, and data listings. The summary tables will be presented separately for Part 1 and Part 2 of the study. All analyses will use SAS version 9.4 or higher.

Continuous variables will be summarized using the number of observations (n), mean, standard deviation (std), median, minimum, and maximum values.

Unless otherwise noted, categorical variables will be summarized by counts and percentages of patients in corresponding categories. Percentages will be rounded to one decimal place except for 100%, which will be displayed without any decimal places, and zero counts, for which the percentage will be displayed as zero percent.

Raw data obtained from eCRFs and transferred from third-part vendors and derived data will be included in data listings.

13.1 Subject Disposition

The number and percentage of patients with informed consent, screened, screen failure, randomization failure, randomized/enrolled, and analysis population will be presented, together with the number and percentage of patients who withdraw from the study prematurely and are excluded from a particular analysis population, and a breakdown of the corresponding reasons.

A tabulation of the number and percentage of patients randomized/enrolled at each center will also be presented.

13.2 Protocol Deviations

The study team and the sponsor will conduct on-going reviews of the deviation data throughout the study. The PP population must be identified prior to database lock.

Sponsor: Lupin Inc.
Protocol no: TB-DPI-301

Protocol deviation data will be categorized into one of the following categories:

- 01-Inclusion/Exclusion/Randomization Criteria
- 02-Continuation Criteria
- 03-Spirometry Evaluation
- 04-Study Procedures
- 05-Study Drug
- 06-Out of Window Visits
- 07-Informed Consent
- 08-Prohibited / Restricted Medications
- 09-Other
- 10-Diary
- 11-ICH/GCP

Each deviation will be further classified as major/minor as defined in the protocol deviation guidelines. A summary of the number of patients with major deviations will be presented by category and treatment for Part 1 and Part 2 of the study separately. All protocol deviation data will be listed.

13.3 Treatments

13.3.1 Extent of Study Drug Exposure

Summary statistics for study drug exposure for Part 1 include:

- Patients exposed to one or more treatments (1, 2 or 3)
- Patients exposed to a specific treatment (Lupin Tiotropium, SPIRIVA HANDIHALER or Placebo)

Summary statistics for study drug exposure for Part 2 include:

- Days of exposure

13.3.2 Prior and Concomitant Medications

A prior medication is defined as any medication started and stopped prior to the first randomized dose.

A concomitant medication is defined as any medication taken on or after the first randomized dose regardless of start day.

All medications will be coded using the WHO Drug Dictionary (version of September 2016), and Anatomical Therapeutic Chemical (ATC) classification system.

Prior and concomitant medications will be summarized by ATC classification for Part 1 and only concomitant medications will be summarized for Part 2. All prior and concomitant medications will be listed.

Sponsor: Lupin Inc.
Protocol no: TB-DPI-301

13.4 Demographic and Baseline Characteristics

Patient demographic and baseline characteristics will be summarized by treatment for the safety population, ITT population, PP population, and Part 2 of the study respectively and will include summary statistics for sex, age, age group (40 to <65, 65 to <75, ≥ 75), race, ethnicity, baseline height (cm), baseline weight (kg) and tobacco usage.

13.5 Medical History

Medical history will be summarized for Part 1 only. All medical history will be listed.

13.6 Efficacy Analyses

13.6.1 Primary Variable

The primary variable is the baseline-adjusted FEV₁ AUC_{0-24h} on the single-dose treatment days. Baseline is defined as the average of the FEV₁ values recorded at approximately 30 minutes and 15 minutes before dosing with study medication.

This crossover study will follow a Williams design with 6 treatment sequences balanced for first order carryover effects (see [Table 1](#)).

A repeated measures crossover model consisting of effects of treatment, period, and sequence will be carried out.

The SAS code for the model is as follows:

```
proc mixed data= final;  
    class usubjid period treatment sequence;  
    model Baseline-adjusted FEV1 AUC0-24h = treatment period sequence /  
solution ddfm=SAT;  
    repeated period /type = un subject = usubjid;  
    lsmeans treatment / alpha=0.05 cl diff;  
run;
```

where

- usubjid = patient
- period = treatment period
- sequence = treatment sequence

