The goal of the study is to complete 180 patients per protocol. With a sample size in each of the 6 sequence groups of 30, for a total sample size of 180, a crossover design will have 90% power to reject both the null hypothesis that the ratio of the test mean to the standard mean is below 0.80 and the null hypothesis that the ratio of test mean to the standard mean is above 1.25 (ie, that the test and standard are not equivalent), in favor of the alternative hypothesis that the means of the 2 treatments are equivalent, assuming that the expected ratio of means is 1.00, the between-patient CV is 1.21, the intra-patient CV is 0.60. In order to allow for a potential 30% premature withdrawal rate or loss from the PP population due to protocol deviations, 240 patients will be randomized in total, 40 to each of the 6 treatment sequences.

As no estimates of within-patient variability were available in the public domain, a blinded interim analysis will be conducted in order to assess the within-patient variability. The blinded interim analysis will be done to ascertain if an increase in sample size is necessary maintain 90% power to complete the study with a 90% CI for the relative bioavailability of the Test (T) to the Reference (R) product inside of the pre-specified interval 0.80-1.25. The blinded interim analysis will be discussed in [Section 11.0](#).

Sponsor: Lupin Inc.
Protocol no: TB-DPI-301

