9.2 Baseline-adjusted FEV₁ AUC_{0-24h}

The baseline-adjusted FEV₁ AUC_{0-24h} is defined as the baseline-adjusted area under the curve for forced expiratory volume in 1 second from time zero to 24 hours postdose using the trapezoidal rule based on actual time of measurement.

The baseline FEV₁ will be the average of the 2 predose FEV₁ measurements (30 minutes and 15 minutes pre-dose) at the clinic visit. If one of the predose FEV₁ measurements is missing, or excluded due to poor quality spirometry effort, the other non-missing measurement will be used as baseline. If both predose FEV₁ measurements are missing or excluded, baseline will be treated as missing.

Baseline-adjusted FEV₁ will be calculated as postdose FEV₁ after subtracting the baseline FEV₁ value.

[figure not shown]
The general area under the concentration-time effect curve (AUC) formula by the trapezoidal rule is given below:

$$AUC_{(0-t_n)} = \sum_{i=1}^n \frac{c_i + c_{i-1}}{2} (t_i - t_{i-1})$$

Sponsor: Lupin Inc.
Protocol no: TB-DPI-301

where t_n is the maximum time, n is the number of time points, and c_i is the change in FEV₁ from baseline at time t_i . For AUC calculations t_0 will be the start time of dose administration ($t_0=0$), and c_0 will be 0. AUC calculations will utilize the actual time of spirometry measurements.

Note- the area under the curve that is the primary variable is the area between the baseline value (straight red line and the curve). It is NOT measured from the x-axis.

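### The primary crossover model uses each period's baseline FEV1 only by subtraction; adding it as a covariate would cost almost nothing and could tighten the T/R interval, by an amount the documents do not determine

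*SAP*

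**What the plan says.** SAP 13.6.1 gives the primary model: "A repeated measures crossover model consisting of effects of treatment, period, and sequence will be carried out". Protocol 11.5.4 names the same three effects. The PROC MIXED code in SAP 13.6.1, and the code that produces the Fieller interval in SAP 13.6.2.2, contain treatment, period and sequence with an unstructured covariance over periods, and no baseline term.

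Baseline enters through the endpoint. SAP 9.2 forms every post-dose value "after subtracting the baseline" FEV1 of that visit, which is the average of the 30- and 15-minute predose readings, or a single reading if the other is missing or excluded. The trapezoidal rule is then applied to these differences over 24 hours.

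Nothing else in the plan uses baseline as a covariate. The 2-treatment secondary analysis (SAP 13.6.2.2) only drops placebo, and the two sensitivity analyses in SAP 9.11 only change how missing profile tails are handled. No reason is given for leaving baseline out.

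**The concern.** Subtracting baseline is an adjustment with the slope fixed at 1. It is fully efficient only if, within a patient, a visit whose predose FEV1 is higher by some amount also has a 24-hour mean higher by exactly that amount. Reading error and the variation of one particular morning are unlikely to persist in full for 24 hours. Where they do not, the change score stays correlated with its own baseline, and the baseline error, multiplied by about 24 hours, remains in each AUC. The unstructured covariance describes correlation between periods. It does not estimate how one period's AUC depends on that period's own baseline.

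What is at stake is precision in the T/R interval and in both comparisons with placebo, from measurements already taken at each of visits 2 to 4.

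**Working it through.** **Inputs from the SAP**
- Section 11.4.2: "Test significance level alpha (one-sided) = 0.05"; "Lower equivalence limit = 0.8"; "Upper equivalence limit = 1.25"; power 90%.
- Section 7.1, initial plan: "assuming that the expected ratio of means is 1.00, the between-patient CV is 1.21, the intra-patient CV is 0.60".
- Section 11.5, interim: "the intra-patient CV was 0.3642 and the between-patient CV was 1.210".
- Section 11.5, revised plan: "Assuming an expected ratio of means of 0.90 based on results from the pivotal PK study", giving 238 per-protocol patients.

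**Step 1: reproduce the SAP's figures.** For two one-sided tests on a ratio of means in a crossover, with the reference mean scaled to 1,

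Var(Y_T − θY_R) = [CV_w²(1+θ²) + CV_b²(1−θ)²]/N, at θ = 0.80 and 1.25, with N−2 degrees of freedom.

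At θ = 0.80, N = 238:
- within-patient part: 0.3642² × 1.64 = 0.2175
- between-patient part: 1.21² × 0.04 = 0.0586
- SE = √(0.2761/238) = 0.0341
- (0.90 − 0.80)/0.0341 = 2.94; less the critical value 1.65, this leaves 1.285, so power is 90.0%.

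The 1.25 limit is more than 8 SEs away and does not bind. The same method gives 371, 77 and 220 for ratios 0.88, 1.00 and 1.12 (SAP: 372, 78, 220), and 177 for the initial plan (SAP: 178).

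**Step 2: variance with and without the covariate.** Within patients, let the 24-hour mean FEV1 have SD 1, the period baseline SD k, and their correlation be ρ.
- Change score: variance 1 + k² − 2ρk.
- Covariate-adjusted: variance 1 − ρ².
- Ratio: (1 − ρ²)/(1 + k² − 2ρk).

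The ratio is never above 1. It equals 1 only when k = ρ, that is, when the slope ρ/k is exactly 1. It is also 1 − r², where r is the within-patient correlation of the change score with its own baseline. A simulation of the six-sequence, three-period design (N = 240, 1,500 runs per value) gave T−R variance ratios of 1.00, 0.96, 0.91, 0.84 and 0.75 for r = 0, −0.2, −0.3, −0.4 and −0.5, which matches 1 − r².

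**Step 3: power at N = 238, ratio 0.90.** Multiply the within-patient part (0.2175) by the ratio and hold CV_b at 1.21. The documents give neither k nor ρ, so both are assumed.

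| | ρ = 0.3 | ρ = 0.5 | ρ = 0.7 |
|---|---|---|---|
| k = 1 | 0.91/1.40 = 0.65; 96.4% | 0.75/1.00 = 0.75; 94.8% | 0.51/0.60 = 0.85; 93.0% |
| k = 0.7 | 0.91/1.07 = 0.85; 93.0% | 0.75/0.79 = 0.95; 91.1% | 0.51/0.51 = 1.00; 90.0% |
| k = 0.5 | 0.91/0.95 = 0.96; 90.9% | 0.75/0.75 = 1.00; 90.0% | 0.51/0.55 = 0.93; 91.5% |

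Example, k = 1 and ρ = 0.5: 0.2175 × 0.75 + 0.0586 = 0.2217; SE = √(0.2217/238) = 0.0305; 0.10/0.0305 − 1.65 = 1.63; power 94.8%. In that cell the expected 90% interval narrows from 0.845-0.954 to 0.852-0.947, and N for 90% power falls from 238 to 192. Values of k above 1 would give larger gains.

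**The case against.** The strongest reply is that baseline is already handled: it is subtracted, on the same day, by a rule fixed in advance. The result is neither biased nor exposed to type I error inflation, so this is a preference about efficiency. That description is right, and it sets the weight of the point. It does not make the covariate redundant, because subtraction imposes a slope that the data could estimate.

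A reader might go further and infer that the trial is underpowered because the baseline noise was overlooked. The documents do not support that. SAP 11.2 makes the baseline-adjusted AUC the interim endpoint, so the subtraction noise is already in the variance behind the CV of 0.3642 and the 238 patients. The SAP also plans about 378 randomized with 30% loss. That leaves 378 × 0.70 = 264.6 patients, and power at 264 on the same inputs is 92.5%.

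A reader might also take 15-35% as the established gain. That range needs equal within-patient variances (k = 1), which no passage gives. Continuation criterion 4 (Protocol 6.4) requires predose FEV1 at visits 3 and 4 to stay within 10% of visit 2, with up to three retests (Protocol 9.3.6). This restricts baseline spread, while the post-dose profile has no such limit. It points towards k below 1 and may make the gain modest.

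Finally, 0.3642 comes from each patient's two closest AUCs, a method SAP 11.4.1 itself expects to give too small a sample size. The power figures therefore illustrate the scale of the effect and should not be read as forecasts.

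**Conclusion.** The point holds as a loss of efficiency of unknown size. The primary and Fieller models use baseline only with a slope fixed at 1. Estimating the slope cannot worsen precision beyond the loss of about 2 degrees of freedom, which is negligible here, and it helps unless the true within-patient slope is 1.

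For ρ from 0.3 to 0.7, the T−R variance falls by 15-35% if k = 1, 0-15% if k = 0.7 and 0-7% if k = 0.5. From 90% at 238 patients and ratio 0.90, power becomes about 93-96%, 90-93% or 90-92%. Zero gain is within the plausible range. These figures assume the SAP's CVs and ratio, with the between-patient CV unchanged by adjustment.

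The change is worth making because the planned ratio of 0.90 lies close to the 0.80 limit and the data are already collected. It is not needed for the validity of the primary result.

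**What to change.** Before unblinding, amend SAP 13.6.1 and 13.6.2.2:

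- Add two covariates to the model: (a) the patient's mean predose FEV1 over the periods that patient contributes to the analysis in question, centred at the average over patients in that analysis set; (b) the period's predose FEV1 minus that patient mean. Splitting baseline this way keeps between- and within-patient slopes apart.
- State how (a) is formed in each analysis. A per-protocol patient whose placebo day is excluded has the mean taken over the T and R days. In the 2-treatment secondary analysis it is the mean over T and R for everyone. A period with both predose readings missing has no endpoint and does not contribute.
- Keep the endpoint, the unstructured covariance and the 0.80-1.25 limits.
- Evaluate the T and R LSMeans at the common mean baseline, with both covariates at zero. With centred covariates the existing ESTIMATE statements then need no further term. If baseline were entered uncentred, each statement would need (1−θ) times the common baseline value.
- Keep the present three-term model as a sensitivity analysis.

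The cost is SAP wording, two derived variables and about 2 degrees of freedom, with no new data. SAP 5.0 provides for a final version before database lock, and Protocol section 11 gives the SAP precedence.
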